5.6.2 Immune Response Assessments

Serum antibody responses to pneumococcal polysaccharides induced by vaccination will be measured using 2 standard assays, OPA and multiplexed Meso Scale Discovery (MSD) IgG.

The OPA assay has been developed and qualified by Nexelis, a GCP-compliant central laboratory, to analyze the 24 polysaccharide antigens contained in VAX-24. The OPA assay has been consistently used as the method for measuring the functional capacity of pneumococcal antibodies, as antibodies to pneumococcal PS protect the host by opsonizing pneumococci (marking pneumococci for destruction) for phagocytosis ([Burton and Nahm 2012](#)).

The MSD assay has been developed and qualified by Nexelis to measure IgG responses against the 24 polysaccharide antigens contained in VAX-24. The MSD multiplex electrochemiluminescent assay is an immunoassay platform that allows simultaneous measurement of responses against multiple antigens and has been used to evaluate responses to various pneumococcal conjugate vaccines ([Marchese 2009](#), [Goldblatt 2011](#), [Feysaguet 2019](#), and [Nolan 2020](#)).

The immune responses (as assessed by OPA and IgG assays) against the 20 polysaccharide antigens common to PCV20 and VAX-24 (1, 3, 4, 5, 6A, 6B, 7F, 8, 9V, 10A, 11A, 12F, 14, 15B, 18C, 19A, 19F, 22F, 23F and 33F) will be compared in the various treatment groups (VAX-24 at 3 different dose levels, and the comparator vaccine), and the 4 incremental polysaccharide antigens contained in VAX-24 (2, 9N, 17F and 20B) will be evaluated separately.

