9.6.2 Threshold analyses

For the 4 non-PCV20 serotypes that are in VAX-24, the % of subjects with a ≥ 4 -fold increase in OPA titer will be evaluated using a logistic regression model, with an indicator variable for achieving a ≥ 4 -fold increase in OPA titer as the dependent variable, and treatment group and study site as fixed effects and \log_{10} baseline titer as a covariate. The difference in proportions achieving a ≥ 4 -fold increase in OPA titer in each of the three VAX-24 dose levels group versus the PCV20 and the corresponding 95% CIs will be calculated. If the lower bound of the 95% CI is > 0.1 , the VAX-24 dose will be deemed statistically superior to PCV20.

The percentage of subjects achieving specified thresholds (eg, GMFR ≥ 4 in serotype-specific OPA and IgG, achieving OPA titer of at least serotype-specific LLOQ of the assay), and associated Wilson (score) 95% CI, will be calculated for the Day 29 visit data for each treatment group. A reverse cumulative distribution curve will be provided. Differences between pair-wise treatment groups may be determined via Fisher's exact tests.

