6.1.3. Adjustments for Covariates

The randomization in this study will not be stratified.

The following variables will be used for adjustment in immunogenicity analyses:

- For the Analysis of variance (ANOVA), study site will be included as fixed effect in the model.
- For the Analysis of covariance (ANCOVA) and the logistic regression, study site will be included as fixed effect and the log baseline titer will be included as covariate in the model. In case the model does not converge, the log₁₀ baseline titer will be removed from the model and a footnote explicating the change will be added.

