6.5.2. Threshold analyses

For the 4 non-PCV20 serotypes that are included in VAX-24 (i.e., 2, 9N, 17F and 20B), the adjusted proportion of subjects with a 4-fold increase in OPA titer will be evaluated using the following model:

- Logistic regression, with an indicator variable for achieving a 4-fold increase in OPA titer at Day 29 as the dependent variable, and treatment group and study site as fixed effects and log₁₀ baseline titer as a covariate. Proportion in each treatment group will be presented along their 95%CI. The difference of proportions in each of the three VAX-

24 dose levels group versus the PCV20 will also be presented along the 95% CI. If the lower bound of the 95% CI is >0.1 , the VAX-24 dose will be deemed statistically superior to PCV20.

Following summaries will also be provided for all serotypes:

- OPA titers:
 - Percentages of subjects achieving a 4-fold increase at Day 29 and associated Wilson score 95% CI and difference of proportions between pair-wise treatment groups using Fisher's exact test.
 - Percentages of subjects with titer \geq LLOQ at Day 29 and associated Wilson score 95% CI and difference of proportions between pair-wise treatment groups using Fisher's exact test.
- IgG concentrations:
 - Percentages of subjects achieving a 4-fold increase at Day 29 and associated Wilson score 95% CI and difference of proportions between pair-wise treatment groups using Fisher's exact test.
 - Percentages of subjects with titer \geq LLOQ at Day 29 and associated Wilson score 95% CI and difference of proportions between pair-wise treatment groups using Fisher's exact test.

Following Figures will be provided on the IEP:

- A reverse cumulative distribution curve of OPA titers on Day 1 and Day 29 by treatment groups for each serotype
- A reverse cumulative distribution curve of IgG concentrations on Day 1 and Day 29 by treatment groups for each serotype
- Bar Plot of OPA GMTs at Day 29 from ANOVA model by treatment group and serotype
- Bar Plot of IgG GMCs at Day 29 from ANOVA model by treatment group and serotype
- Bar Plot of percentages of subjects achieving a 4-fold increase in OPA titers by serotype
- Bar Plot of percentages of subjects achieving a 4-fold increase in IgG concentrations by serotype
- Forest Plot of OPA GMRs and GMFRs from ANOVA model at Day 29 for VAX-24 compared with PCV20 by serotype
- Forest Plot of IgG GMRs and GMFRs from ANOVA model at Day 29 for VAX-24 compared with PCV20 by serotype

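### The only non-convergence fallback for the 4-fold-rise logistic model drops baseline and keeps about 20 site effects, so it cannot cure separation from a site or an empty PCV20 arm; the interval behind the >0.1 superiority rule is also unnamed

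*SAP*

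**What the plan says.** - **Model.** SAP 6.5.2 takes serotypes 2, 9N, 17F and 20B and states that "the adjusted proportion of subjects with a 4-fold increase in OPA titer will be evaluated using the following model": a logistic regression with an indicator of 4-fold rise as outcome, "and treatment group and study site as fixed effects", and log10 baseline titer as covariate. Protocol 9.6.2 gives the same model.
- **Decision rule.** Each VAX-24 dose is compared with PCV20 by a difference in proportions. If its lower 95% bound exceeds 0.1, "the VAX-24 dose will be deemed statistically superior to PCV20". On how the difference is obtained, the protocol says only that the differences "versus the PCV20 and the corresponding 95% CIs will be calculated"; the SAP says no more.
- **Fallback.** SAP 6.1.3 covers non-convergence in one sentence: the log10 "baseline titer will be removed from the model and a footnote explicating the change will be added". Treatment and site are untouched. The sentence also covers the ANCOVA, where least squares has no convergence problem.
- **Setting.** The Protocol Synopsis plans about 20 sites. SAP 2.3 plans 200 subjects, 50 per arm, without stratification. SAP 5.3 (pooling) is marked not applicable. Protocol 5.6.2 confirms that these serotypes are not shared with PCV20: "the 4 incremental polysaccharide antigens contained in VAX-24 (2, 9N, 17F and 20B) will be evaluated separately".
- **Beside the model.** SAP 6.5.2 also plans, for all serotypes, "Percentages of subjects achieving a 4-fold increase at Day 29 and associated Wilson score 95% CI", with pairwise Fisher tests.

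**The concern.** About 20 site effects on about 200 subjects leaves roughly 10 subjects per site and 2.5 per arm per site. A small site can easily have all or none of its subjects respond. PCV20 contains none of the four serotypes, so few PCV20 responders can be expected and an arm with none is possible. Either event is separation: a coefficient has no finite maximum likelihood estimate.

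The stated remedy removes the one term that is unlikely to be the cause and keeps those that are. Baseline adjustment is lost and the separation stays.

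The superiority label is then read from a difference in proportions whose estimator and interval are not specified. The SAP defines LS means for GMT/GMC, GMR and GMFR, but not for proportions. Two programmers could follow the SAP faithfully and report opposite labels.

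**Working it through.** **1. Design figures.** 200/4 = 50 per arm, as SAP 2.3 states. 200/20 = 10 per site; 10/4 = 2.5 per arm per site. The documents give no response rates or site sizes, so steps 2 and 4-6 rest on assumptions.

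**2. Empty PCV20 arm.** P(no responder among 50) = (1 - p)^50: 36.4% at p = 2%, 7.7% at 5%, 0.5% at 10%.

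**3. Why the fallback cannot work.** The model is logit P(rise) = arm + site + b x log10 baseline. If a combination of arm and site indicators alone separates responders from non-responders, its weight on baseline is zero, so deleting baseline leaves it intact. In one example dataset with 0/50 on PCV20, the log-odds coefficient for one VAX-24 dose after 5, 12 and 20 Newton steps was 6.6, 13.6 and 21.6 with baseline (SE 3.0, 99.9, 5453). Without baseline it was 6.5, 13.5 and 21.5 (SE 3.1, 100.7, 5500).

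**4. How often separation occurs.** Simulated four-arm trials, 50 per arm, 1,000 per scenario, unstratified. Assumed: log-odds -0.7 per SD of log10 baseline titer, no site effect, PCV20 5% or 10%, VAX-24 70% or 80%.

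| Site sizes | Trials with separation |
|---|---|
| 20 sites of 10 | 6%-25% |
| 20 sites, chance variation in size | 24%-47% |
| Uneven: 4x26 + 6x10 + 6x4 + 4x3 = 200 | 88%-93% |
| 10 sites | 1%-8% |

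The first three rows are 12 large-effect scenarios with 5,684 separated datasets. Of these, 5,229 had an all-or-none site, 495 an all-or-none arm (some had both), and 159 were separated by site and arm jointly. So 5,684 - 159 = 5,525 had an all-or-none site or arm.

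**5. Does the fallback cure it?** Adding 5% v 15%, 10% v 20% and 10% v 40% under the same three site patterns gives 21 scenarios and 13,429 separated datasets. Dropping baseline cured 0. Dropping site cured 12,650; the other 13,429 - 12,650 = 779 all had an arm with none or all responding. Steeper baseline slopes barely change this: dropping baseline cured 0 of 414 at -2 per SD and 9 of 408 at -4 per SD.

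**6. What the unnamed estimator does.** P(lower bound > 0.1) in datasets with an all-or-none site or arm. The proposed rule uses the full model if there is no separation, the model without site if there is, and Newcombe if either compared arm is all-or-none.

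| True difference | SAP fallback, LS means averaged equally over sites | SAP fallback, marginal standardisation | Proposed rule |
|---|---|---|---|
| 60-75 points | 5.0% (275/5,525) | 99.9% (coverage 90.1%) | 99.98% (coverage 93.9%) |
| 10% v 40% | 0.2% (4/1,810) | 70.1% | 73.0% |
| Exactly 0.10 (nominal 2.5%) | 0% | 2.9% | 2.4% |

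The LS-means failure is specific to separation: in large-effect datasets without it, LS means passed in 100%.

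Over all simulated data:
- Proposed rule: coverage 91%-95%, false superiority 1.4%-2.9%.
- Site always kept, with standardisation: coverage 87%-94%, false superiority 2.3%-4.5% (pooled 206/6,000 = 3.4%).
- Newcombe: coverage 94%-97%, false superiority 1.3%-2.5%.

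**7. Limit of the check.** The fits used a Newton routine (relative gradient 1e-8, at most 25 steps), not SAS. It declared convergence in every separated dataset of the 21 scenarios. The fallback columns therefore show what happens if the fallback is applied, not how often SAS would apply it.

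**The case against.** - **The fallback may never be invoked.** It is triggered by non-convergence, and the routine used here reported convergence despite separation. This stands. The separation would then go untreated, which is why the fix must be triggered by detected separation as well.
- **The zero cure count is algebra, not evidence.** Largely true. What the simulation adds is that baseline is rarely the cause, even with steep slopes.
- **The label is lost only under one estimator.** Correct: marginal standardisation of the same fallback model keeps it, and an all-or-none site leaves the treatment log-odds contrast estimable. So most of the consequence comes from the unnamed estimator. The LS-means error is missed superiority, not a false claim. Among crude intervals the choice matters only near the boundary: with 0/50 on PCV20, the smallest passing VAX-24 count is 10 (Miettinen-Nurminen), 11 (Wald, Newcombe) or 12 (Agresti-Caffo).
- **Frequency is assumed.** Separation ranges from 1% to 93% across the assumed settings. This shows that it is plausible, not how likely it is.
- **Stakes are low.** The sample size was not set for hypothesis tests, 4-fold rise is not a listed primary or secondary endpoint, and the crude summaries survive separation. This limits the severity. However, Fisher's test gives no bound to set against 0.1, and the Wilson intervals are for single arms.
- **Newcombe alone covers better.** True, but at 10% v 40% its power is 67%-68%, against 74%-75% for the proposed rule.

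**Conclusion.** The concern holds, as a minor point. That the fallback cannot remove separation carried by a site or an all-or-none arm follows from the model and needs no assumed rates; it could help only if baseline itself separates. The missing estimator and interval are plain from SAP 6.5.2 and Protocol 9.6.2.

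The size of the effect depends on the assumed response rates, baseline slope, site sizes and absence of site effects. Under those assumptions, in large-effect datasets with an all-or-none site or arm, the fallback yields the superiority label in 5.0% or 99.9% of cases according to an unstated choice. The version that keeps the label has about 90% coverage. Confidence is medium, mainly because the frequency of separation is unknown and SAS behaviour was not tested.

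**What to change.** 1. **SAP 6.1.3.** For the logistic model, replace the fallback with: if separation is detected or the model does not converge, remove study site, keep log10 baseline titer, and footnote the change. If either arm of a comparison has no responders or only responders, use the unadjusted Newcombe interval for that difference.
2. **SAP 6.5.2.** State that the adjusted difference is obtained by marginal standardisation with a delta-method 95% CI, that the >0.1 rule is read from that interval, and that the unadjusted Newcombe interval is shown beside it.

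**Cost.** SAP wording and programming only. Site adjustment is lost whenever the fallback applies, and the model may differ among the four serotypes. With very uneven sites the model without site could become the usual analysis, so the departure from the model in Protocol 9.6.2 should be recorded in SAP Section 7. Site is not a stratification factor, which makes its loss easier to accept.

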6.1.4. Multiple Comparisons/Multiplicity

Since there are no formal hypothesis tests in this study, no adjustment for multiplicity will be made.

6.1.5. Subgroups

There is no plan for subgroup analysis at this stage.

6.1.6. Missing, Unused, and Spurious Data

Binary endpoints / Continuous data:

Missing data are assumed to be missing at random and ignorable. Missing data will not be estimated or imputed. Denominators for percentages will be based only on the number of subjects with non-missing values. The only exception is:

- Systemic Solicited AEs with missing "Relationship to study vaccine" will be analyzed as "Possibly related".

Dates:

For partial or missing AE start dates the following imputation rules will be applied:

1. If year is not missing and is after the year of first dose:
 - a. If month is missing, then month will be imputed as January.
 - b. If day is missing, then day will be imputed as the first of the month.
2. If year is not missing and is the same as the year of the first dose:
 - a. If month is missing, then impute the month as the month of the first dose date.
 - b. If day is missing, and the month is the same as the month of the first dose date, then impute day as the day of the first dose date.
 - c. If day is missing but month is after the month of first dose date, then impute day as the first day of the month.
3. If year is missing, then impute the year as the year of the first dose date:
 - a. If month is missing, then impute the month as the month of the first dose date.
 - b. If day is missing, then impute the day as the day of the first dose date.
4. If the start date is completely missing, but the AE is either ongoing (i.e. AE stop date is missing) or the stop date is after the first dose date then impute the start date as the first dose date.
5. For any cases involving the rules above, if the AE end date is before the AE start date, then do not impute the AE start date and assume that the AE is treatment emergent/concomitant for the purpose of the analysis. Further, if the AE stop date occurs prior to the first dose date, do not impute the AE start date, and assume that the AE is not treatment emergent.

No imputations will be applied to AE stop dates or other dates. As indicated above, AEs with missing stop date are considered ongoing.

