6.4.1.2. Unsolicited Adverse Events

An unsolicited AE is an AE that is spontaneously reported by the subject or discovered by the Investigator. SAEs, NOCIs and MAAEs would be recorded as part of the collection of unsolicited AEs as specified in the visit procedures. Unsolicited AEs are collected separately from solicited AEs.

Solicited AEs continuing beyond 7 days will be flagged using rules given in Section 5.2 and described in separate summaries as explained in Section 6.4.1.3.

The definition of a treatment emergent AE (TEAE) is an event that occurs after vaccination and within the 28 days after vaccination (i.e., excluding those after a subject has given informed consent, but before vaccination):

- Onset (days) = Start date of AE – Date of Study Vaccine Administration + 1
- An AE is a TEAE if Onset \geq 1 and Onset \leq 28

Adverse events are summarized by subject, therefore, in any tabulation, a subject contributes only once to the count for a given adverse event (SOC or preferred term).

Unsolicited AEs will be coded using the Medical Dictionary for Regulatory Activities (MedDRA) and will be summarized by decreasing frequency of SOC and preferred term within SOC in the control group, as follows:

- Any unsolicited TEAEs
- Possibly or probably related unsolicited TEAEs
- Unsolicited TEAEs leading to study withdrawal
- Any AE leading to death
- Any SAE within 6 months after the vaccination by maximum relationship to study treatment. This summary will include serious solicited AEs.
- Any NOCI within 6 months after the vaccination by maximum relationship to study treatment.
- Any MAAEs within 6 months after the vaccination by maximum relationship to study treatment.

Following by-subject Listings will be provided:

- Pre-vaccination AEs (non-emergent)
- All unsolicited TEAEs
- All post-vaccination SAEs, NOCIs and MAAEs

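### SAP date rule 3 conflicts with rules 1b, 2c and 4: an AE with no year can be imputed to Day 29–32, or to before vaccination across a year end

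*SAP*

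**What the plan says.** SAP 6.1.6 gives five rules for partial or missing AE start dates.

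- Rule 1b (year known, later than the dose year): "If day is missing, then day will be imputed as the first of the month".
- Rule 2b (dose year and dose month known, day missing): the dose day is used.
- Rule 2c (dose year known, later month): "If day is missing but month is after the month of first dose date, then impute day as the first day of the month".
- Rule 3: "If year is missing, then impute the year as the year of the first dose date". A missing month becomes the dose month (3a). For the day, 3b reads "If day is missing, then impute the day as the day of the first dose date". Neither the year nor the day depends on which month was recorded.
- Rule 4 (no part of the start date known, and the event either continuing or stopping later than vaccination): the start is put on the dose date.
- Rule 5 grants treatment-emergent status when the recorded end precedes the imputed start; its wording includes "if the AE end date is before the AE start date, then do not impute the AE start date and assume that the AE is". The section adds that "AEs with missing stop date are considered ongoing".

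SAP 6.4.1.2 computes onset as start date minus vaccination date plus 1. "An AE is a TEAE if Onset" lies between 1 and 28. The unsolicited AE tables (any, related, leading to withdrawal) and the combined tables in SAP 6.4.1.3 are limited to TEAEs. The SAE, NOCI and MAAE tables instead cover six months from vaccination.

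**The concern.** Rules 1 and 2 resolve uncertainty towards the earliest date after vaccination that the recorded information allows. Rule 3 does not. It carries the dose day into a later month, which adds about one calendar month to the dose date and so just clears a 28-day window. It also fixes the year without asking whether the result is possible.

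The outcome is also illogical beside rule 4. An ongoing AE with no start date at all is put on Day 1 and counted. The same AE with a later month recorded can be excluded, so knowing more about an event can remove it.

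At stake are the unsolicited AE percentage, a primary safety endpoint in SAP 3.2, and, in the year-end case only, the 6-month SAE, NOCI and MAAE percentages, which are primary too.

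**Working it through.** The plan states no figure for these rules, so there is none to reproduce. The check is date arithmetic on the SAP's own rules and onset formula.

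**Case A: day and year missing, recorded month is the next month in the same year.** Rule 3b gives the dose day in the following month.

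- Example: dosed 20 March, AE recorded as April. Rule 3b gives 20 April: 31 + 1 = Day 32. Rule 2c would give 1 April: 12 + 1 = Day 13.
- All January–November dose dates in a 365-day year (334), with an impossible day capped at month end (an assumption): Day 29 on 29 dates, Day 30 on 1, Day 31 on 125 and Day 32 on 179. The sum is 334, and none is Day 28 or earlier.
- Rule 2c on the same dates gives Day 28 or earlier on 297. On the other 37, even the first of the next month is past Day 28, so rule 2c loses no true TEAE.

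**Case B: year missing, true onset in the calendar year after dosing.**

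- Day and month recorded: dosed 10 December (day 344 of the year), AE 3 January. Rule 3 gives 3 - 344 + 1 = Day -340. The true value is (365 + 3) - 344 + 1 = Day 25.
- Day also missing: dosed 20 December, AE recorded as January. Rule 3 gives 20 January of the dose year, Day -333. Rule 1b with the correct year gives 1 January, Day 13.
- Rule 5 cannot help, because a stop date after vaccination is not before the imputed start.

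**Records that rule 3 handles acceptably.** If the recorded month is the dose month and the day is missing, the imputed date is the dose date, Day 1, and the AE is kept. If day and month are both recorded, the date is correct unless a year end intervenes.

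**How far rule 5 rescues Case A.** Assumptions not in the documents: dose dates uniform over a calendar year, true onsets uniform over Day 1–28, day and year missing with month recorded, and stop date equal to onset plus duration.

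| Stop date | Next-month, same-year AEs kept by rule 5 | All true Day 1–28 AEs with this pattern that are lost |
|---|---|---|
| 3 days after onset | 95% | 5.6% |
| 7 days | 69% | 16.3% |
| 14 days | 33% | 30.9% |
| 28 days | 0.4% | 44.2% |
| Missing | 0% | 44.4% |

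The 44.4% is 40.7% imputed too late plus 3.7% imputed before vaccination; the other 55.6% stay at Day 1. With no December dosing the 3.7% disappears.

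**Six-month endpoints.** With the year missing and true onset uniform over Day 1–180, none are imputed before vaccination for January–June dosing and 48.6% are for July–December dosing.

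Every percentage is conditional on the missing-date pattern. None estimates its effect on a reported AE rate.

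**The case against.** The strongest objection is that the trigger hardly ever occurs. Protocol 7.5.2 lists start and stop dates among the items for every AE, AEs are reviewed at Day 8 and Day 29, SAEs are reported within 24 hours, and queries are resolved before the study is complete. Participation lasts at most 211 days (Protocol 3.3), so a recorded month fixes the year and a site query would settle it. An onset near Day -340 would predate consent and stand out in the pre-vaccination listing. The rules are the same in all arms. All of this stands as to size. It does not make the rule right for records that still lack a year, since the tables would follow the rule as written.

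Four stronger readings are tempting, and the documents do not support them.

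- *Any AE without a year falls out.* It does not: dose-month AEs stay at Day 1, and those with day and month recorded fail only across a year end.
- *No next-month AE survives.* That ignores rule 5, which keeps most short events that have a recorded stop date.
- *The error always lowers the AE rate.* Dosed 20 March, an AE recorded as May, truly 5 May (Day 47) and ending 10 May, is imputed to 20 May. Rule 5 then calls it treatment emergent, a false inclusion.
- *All safety tables are affected.* An imputation to Day 29–32 does not remove an event from the SAE, NOCI, MAAE or death summaries, which are not limited to TEAEs. Solicited AEs go by diary page (SAP 5.2).

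**Conclusion.** The point holds in a limited form. Rule 3 misclassifies two kinds of record: a next-month AE with day and year missing, unless rule 5 applies, and an AE with the year missing whose onset falls in the calendar year after dosing. The first leaves only TEAE-based tables; the second also leaves the 6-month counts. This rests on a literal reading of SAP 6.1.6 and on date arithmetic. Only the shares in the table and the 6-month percentages need the uniformity and duration assumptions.

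The effect on reported rates cannot be computed, because the documents give neither dosing dates nor the frequency of a month without a year. It is likely small. This is a minor correction, worth making because the rule contradicts its neighbours and is cheap to repair.

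**What to change.** In SAP 6.1.6, when the month is recorded but the year is missing, set the year so that the month falls between informed consent and the Month 6 contact. Then impute a missing day by rule 1b, 2b or 2c. Keep the dose month and day only when month and year are both missing. Leave rules 4 and 5 unchanged.

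Bounding the year by consent matters because SAEs are reported from consent (Protocol 7.5.1). Taking the first occurrence of the month on or after dosing would push a screening-period SAE forward by almost a year. A span of at most 211 days contains a given month in only one year, so the choice is unambiguous.

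Applied to the same enumeration, this keeps every true Day 1–28 onset in the window. The cost is about two sentences and a small programming change before database lock. The downside is that an AE of uncertain date may occasionally be counted as a TEAE, which rules 1 and 2 already allow.
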